8.3.3.2. Other Comparisons of Interest

If one or both of the primary endpoints is considered statistically significant, inferences will be made from unadjusted p-values for treatment comparisons on secondary and other endpoints. If both co-primary treatment comparisons are statistically significant, these secondary and other treatment comparisons will be declared significant if the unadjusted p-value is <0.05 . If only one co-primary treatment comparison is statistically significant, these secondary and other treatment comparisons will be declared significant if the unadjusted p-value is <0.01 .

Where strong control of type I error is required for secondary endpoints, multiplicity will be controlled using a hierarchical, closed testing procedure. The secondary hypothesis tests will be grouped sequentially in two blocks of two comparisons each, grouped according to specific clinical concepts (lung function and symptoms, and time-to-first exacerbation event). Each block of comparisons will also be adjusted for multiplicity using the truncated Hochberg method as described for the primary endpoint analysis, with a truncation parameter of $\gamma=0.6$ for the first block and a truncation parameter of $\gamma=1$ for the second block.

Within each block, at least one endpoint must be considered statistically significant in order to make inferences in the subsequent block. For example, as shown in [Figure 2](#) at least one of endpoints S1a and S1b would need to be significant in order to make inferences for the S2a/S2b comparisons contained in the next block.

Figure 2 Secondary endpoint hierarchy

Methods for handling missing data for summaries of the secondary efficacy endpoints will be detailed in the RAP.

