Secondary and Other Analyses	
 
• Pairwise comparisons of FF/UMEC/VI versus FF/VI and FF/UMEC/VI versus UMEC/VI will be performed for the secondary efficacy and other endpoints.
 
• If at least one of the co-primary treatment comparisons is considered statistically significant, inferences will be drawn from p-values for the secondary and other treatment comparisons.
 
• If both co-primary treatment comparisons are statistically significant, these secondary and other treatment comparisons will be declared significant if the unadjusted p-value is <0.05. If only one co-primary treatment comparison is statistically significant, these secondary and other treatment comparisons will be declared significant if the unadjusted p-value is <0.01.
 
• If neither of the co-primary treatment comparisons is considered statistically significant, testing on the secondary and other endpoints will be performed and presented for descriptive purposes only.
 
• No adjustment for multiplicity will be made across these secondary and other treatment comparisons.
 

Secondary and Other Analyses where strong control of type I error is required	
 
• Where strong control of type I error is required, multiplicity will be controlled across selected secondary endpoints and treatment comparisons using a hierarchical, closed testing procedure. The secondary hypothesis tests will be grouped sequentially in two blocks of two comparisons each, grouped according to specific clinical concepts (lung function and health-related quality of life, and time to first exacerbation event).
 
• Each block of comparisons will also be adjusted for multiplicity using the truncated Hochberg method as described for the primary endpoint analysis with a truncation parameter of <math>\gamma=0.6</math> for the first block and a truncation parameter of <math>\gamma=1</math> for the second block.
 

Overview	Key Elements of the RAP

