	

• Within each block, at least one endpoint must be considered statistically significant in order to make inferences in the subsequent block.

• If at least one endpoint is statistically significant in the final block, inferences will be drawn from p-values for the remaining secondary and other treatment comparisons. The reference level for declaring statistical significance will depend on the results obtained from tests within the hierarchy.

• If neither of the treatment comparisons in the final block is considered statistically significant, testing on the remaining secondary and other endpoints will be performed and presented for descriptive purposes only.

• No adjustment for multiplicity will be made across the remaining secondary and other treatment comparisons.

• In addition, pairwise comparisons of UMEC/VI and FF/VI will be performed for all endpoints. These are not adjusted for multiplicity.

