## 2.4. Statistical Hypotheses

The primary purpose of this study is to evaluate the efficacy of FF/UMEC/VI to reduce the annual rate of moderate/severe exacerbations compared with dual therapy of FF/VI or UMEC/VI in subjects with COPD over a 52 week period.

The aim of this study is to demonstrate the contribution of the inhaled corticosteroid (ICS (FF)) when used in combination with a fixed dose of a long-acting beta-agonist / long-acting muscarinic receptor antagonist (LABA/LAMA (UMEC/VI)), and the contribution of the LAMA (UMEC) above the efficacy of an ICS/LABA (FF/VI) combination, in reducing the rate of on-treatment moderate/severe exacerbations in subjects with COPD.

The primary endpoint is the annual rate of on-treatment moderate/severe exacerbations (calculated from the number of moderate and severe exacerbations during the treatment period).

The primary analyses will be the pairwise comparisons of FF/UMEC/VI with FF/VI and FF/UMEC/VI with UMEC/VI, with inferences adjusted for multiplicity as described in Section 11.9. The primary analyses will be based on a two-sided hypothesis testing approach.

The hypotheses associated with the statistical test of the primary efficacy endpoint are:

$$H_0: \lambda_T/\lambda_D=1 \text{ versus } H_A: \lambda_T/\lambda_D \neq 1$$

where  $\lambda_T$  is the annual rate for triple therapy (FF/UMEC/VI) and  $\lambda_D$  is the annual rate for the respective dual therapies (FF/VI and UMEC/VI).

In addition the comparison of UMEC/VI with FF/VI will be presented on all analysis tables with the exception of the Jump to Reference sensitivity analyses.

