## 11.9. Appendix 9: Handling Multiple Comparisons and Multiplicity

The study has been powered at the 1% significance level in order to satisfy regulatory requirements of substantial evidence of efficacy for a single study. However, type I error is controlled at the 5% significance level.

In order to account for multiplicity, the truncated Hochberg procedure (Dmitrienko, 2008) with a truncation parameter of  $\gamma=0.6$  will be used to control overall type I error at  $\alpha=0.05$ .

For the co-primary treatment comparisons (pairwise comparison of FF/UMEC/VI with FF/VI and FF/UMEC/VI with UMEC/VI for the annual rate of on-treatment moderate/severe exacerbations), both comparisons will be declared statistically significant if the unadjusted p-value for both comparisons is significant at the 0.04 level. Should the largest p-value for the two comparisons be above 0.04, the other comparison will be declared statistically significant if the smaller unadjusted p-value is below 0.025.

Pairwise comparisons of FF/UMEC/VI versus FF/VI and FF/UMEC/VI versus UMEC/VI will be performed for the secondary efficacy and other endpoints and for UMEC/VI vs. FF/VI on all endpoints. These comparisons will not be adjusted for multiplicity. If at least one of the co-primary treatment comparisons is considered statistically significant, inferences will be drawn from p-values for the treatment comparisons on secondary and other endpoints. If neither of the co-primary comparisons is considered statistically significant, testing on the secondary and other endpoints will be performed and presented for descriptive purposes only.

[figure not shown]
If both co-primary treatment comparisons are statistically significant, these secondary and other treatment comparisons will be declared significant if the unadjusted p-value is  $<0.05$ . If only one co-primary treatment comparison is statistically significant, these secondary and other treatment comparisons will be declared significant if the unadjusted p-value is  $<0.01$ .

Where strong control of type I error is required, multiplicity across selected treatment comparisons and secondary endpoints will be controlled using a hierarchical, closed testing procedure. The secondary hypothesis tests will be grouped sequentially in two blocks of two comparisons each, grouped according to specific clinical concepts (lung function and symptoms, and time to first exacerbation event).

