**Figure 1 Secondary endpoint hierarchy**

Note that the reference level required to determine statistical significance for each block within the secondary hierarchy will depend on whether one or both comparisons were significant at the prior step:

	Reference level for statistical significance based on unadjusted p-value for comparisons of FF/UMEC/VI versus FF/VI (all co-primary, block 1 and block 2 endpoints) and FF/UMEC/VI versus UMEC/VI (co-primary and block 2 endpoint)			
Co-primary treatment comparisons	Both $p < 0.04$	Both $p < 0.04$	One $p \geq 0.04$ and one $p < 0.025$	One $p \geq 0.04$ and one $p < 0.025$
Block 1	Both $p < 0.04$	One $p \geq 0.04$ and one $p < 0.025$	Both $p < 0.008$	One $p \geq 0.008$ and one $p < 0.005$
Block 2	Both $p < 0.05$ or One $p \geq 0.05$ and one $p < 0.025$	Both $p < 0.01$ or One $p \geq 0.01$ and one $p < 0.005$	Both $p < 0.008$ or One $p \geq 0.008$ and one $p < 0.005$	Both $p < 0.002$ or One $p \geq 0.002$ and one $p < 0.001$

All further efficacy endpoints/treatment comparisons not in the above testing hierarchy will be considered statistically significant at the relevant reference level as detailed in Block 2 if at least one treatment comparison is considered to be statistically significant in Block 2.

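### Endpoints outside the hierarchy can be called statistically significant under the strong-control heading after one Block 2 win, when no alpha is left to cover them

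*SAP*

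**What the plan says.** The co-primary rule in SAP 11.9 is truncated Hochberg with γ=0.6: "both comparisons will be declared statistically significant if the unadjusted p-value for both comparisons is significant at the 0.04 level"; failing that, "the other comparison will be declared statistically significant if the smaller unadjusted p-value is below 0.025". The tests are two-sided (SAP 2.4: "The primary analyses will be based on a two-sided hypothesis testing approach"), and SAP 11.9 gives the overall standard: "However, type I error is controlled at the 5% significance level".

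Two secondary blocks of two comparisons follow. Block 1 (trough FEV1 and SGRQ total score at Week 52 versus FF/VI) uses γ=0.6. Block 2 (time to first moderate/severe exacerbation versus each dual therapy) uses, in Protocol 8.3.3.2, "a truncation parameter of $\gamma=1$ for the second block"; SAP 11.9 gives the same value. A table under Figure 1 of SAP 11.9 sets out the levels for each pattern of wins.

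Below that table, all further efficacy endpoints and comparisons "will be considered statistically significant at the relevant reference level as detailed in Block 2 if at least one treatment comparison" in Block 2 is won. The SAP synopsis has a matching statement in the row headed "Secondary and Other Analyses where strong control of type I error is required": "If at least one endpoint is statistically significant in the final block, inferences will be drawn from p-values for the remaining secondary" and other comparisons, at a level that depends on the hierarchy results. The same row confines strong control to selected secondary endpoints and says that the remaining comparisons are not adjusted among themselves.

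Separately, Protocol 8.3.3.2, another synopsis row and SAP 11.9 describe an openly unadjusted route. There, secondary and other endpoints are judged at 0.05 or 0.01 according to whether both or one of the co-primaries won.

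**The concern.** A γ of 1 is the natural choice for the last family in a gatekeeping sequence, because nothing needs to be passed on. Protocol 8.3.3.2 ends the hierarchy at Block 2. The SAP adds a further step after it, opens that step on a single Block 2 win, and reuses the Block 2 level. This step is not among the changes from the protocol listed in SAP 2.1.

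The comparisons affected are listed secondary endpoints: severe exacerbation rate versus FF/VI and versus UMEC/VI, and exacerbation rate and time to first exacerbation versus UMEC/VI in the subset with eosinophils of at least 150 cells/µl. The subset is a stated secondary objective. A reader told that one of these is statistically significant, by a rule placed under the strong-control heading, would reasonably take it as covered by the 5% error rate.

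**Working it through.** **Rule.** For two comparisons at block level α, truncated Hochberg tests the larger p-value against [γ+(1−γ)/2]α and the smaller against α/2. The alpha passed on is α after two wins, α−[γ+(1−γ)/2]α after exactly one, and 0 after none.

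**The plan's own levels.** With γ=0.6 the bracket is 0.6+0.2=0.8. Co-primaries: 0.8×0.05=0.04 and 0.05/2=0.025, as printed. One win passes on 0.05−0.04=0.01. Block 1 at 0.01 gives 0.008 and 0.005, as printed, and one win there passes on 0.01−0.008=0.002. With γ=1 the bracket is 1, so Block 2 becomes:

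| Column | Wins: co-primary, Block 1 | α entering Block 2 | Levels at γ=1 | Printed | Left after exactly one Block 2 win |
|---|---|---|---|---|---|
| 1 | both, both | 0.05 | 0.05 / 0.025 | same | 0.05−0.05=0 |
| 2 | both, one | 0.01 | 0.01 / 0.005 | same | 0.01−0.01=0 |
| 3 | one, both | 0.01 | 0.01 / 0.005 | 0.008 / 0.005 | 0.002 at the printed level |
| 4 | one, one | 0.002 | 0.002 / 0.001 | same | 0.002−0.002=0 |

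Every level reproduces except column 3 of Block 2, which shows the γ=0.6 value. That entry is conservative. Even there, the 0.002 left is below the 0.008 or 0.005 that would be reused.

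**Inside the hierarchy.** With only the two co-primary nulls true and independent tests, the error is 0.04²+2×0.025×0.96=0.0016+0.048=0.0496. The six tests were also simulated at the printed levels over all combinations of true nulls and two effect sizes (126 scenarios per correlation; correlations 0, 0.3 and 0.6). The largest familywise error at each correlation was 0.0506 to 0.0516. The Monte Carlo standard error is about 0.0009, so these maxima are consistent with 0.05.

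**Beyond Block 2.** Take column 1, with one Block 2 null true, the other comparison clearly won, and K null outside endpoints tested at level L. Because the other comparison is won, the null Block 2 comparison is falsely rejected with probability 0.05. If it is not, exactly one comparison has won and the outside endpoints open. With independent tests, familywise error = 1−0.95×(1−L)^K:

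| K | L=0.025 | L=0.05 |
|---|---|---|
| 1 | 1−0.95×0.975=7.4% | 1−0.95²=9.75% |
| 4 | 1−0.95×0.975⁴=14.1% | 1−0.95⁵=22.6% |

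K=4 stands for the four remaining listed secondary comparisons. Simulation at correlation 0.5 gives 11.7% and 18.3% for K=4.

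**Both Block 2 effects real.** The full 0.05 remains, but each outside endpoint uses it: four nulls give 1−0.95⁴=18.5% if independent.

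**The case against.** The strongest reply is that the SAP never promises strong control for these endpoints. The synopsis limits it to selected secondary endpoints and disclaims adjustment across the rest. SAP 11.4.3 gives adjusted p-values only to endpoints in the hierarchy, and SAP 8.4 to 8.6 specify unadjusted p-values for the severe-exacerbation and eosinophil analyses. All of that stands.

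For the same reason, a reader might infer that the strong-control procedure as a whole fails. The documents do not support this: nothing tested after Block 2 can alter the error rate within the six tests, and that rate is held. Nor is γ=1 the only cause, since 18.5% arises with both Block 2 effects real. That part of the inflation comes from the disclosed choice not to adjust among outside endpoints.

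It is also fair that the illustration uses column 1, where levels are highest, and that 22.6% is the upper end. It needs independence, and 0.05 rather than 0.025 after one win. Block 2 and the eosinophil-subset comparisons share subjects and events, so independence is unlikely.

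The reply does not dispose of the point. Declining to adjust across the remaining endpoints does not justify declaring even one of them significant once no alpha remains. A level said to depend on results within the hierarchy reads as alpha carried forward, not as nominal reporting. The SAP already has a separate unadjusted route, so the extra step is not needed for that purpose.

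**Conclusion.** The point holds for the extension beyond Block 2 only. After exactly one Block 2 win, γ=1 leaves nothing to pass on (columns 1, 2 and 4 as printed), yet every outside endpoint may be declared significant at a Block 2 level that is not specified. After two wins, each may use the whole block alpha.

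The sizes rest on column 1, four remaining listed secondary comparisons all truly null, and independent or equicorrelated normal test statistics. Positive correlation lowers the figures. The SAP lists many more outside endpoints, so four is not the largest possible number. The co-primary, Block 1 and Block 2 conclusions are unaffected.

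**What to change.** Replace the sentence below the reference-level table in SAP 11.9, and its counterpart in the synopsis strong-control row, with: *Within the strong-control procedure, endpoints and comparisons outside the co-primary, Block 1 and Block 2 tests are reported with nominal p-values and are not declared statistically significant, whatever the Block 2 result.* This covers both the one-win and the two-win case and removes the question of which level applies.

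Also reconcile the column 3 Block 2 entry: γ=1 gives 0.01/0.005, while 0.008/0.005 is printed.

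The cost is two sentences and one table entry. No data collection or primary analysis changes. Fewer endpoints could be labelled significant under the strong-control route; the separate, openly unadjusted route is untouched. If declarations on the four remaining secondary comparisons are wanted under strong control, they would need both Block 2 wins plus an adjustment. In column 1, Bonferroni over the four gives 1−(1−0.0125)⁴=4.9% when both Block 2 effects are real and the tests are independent; simulated error was about 0.049 to 0.050, whether one or both Block 2 effects were real.

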## 11.10. Appendix 10: Model Checking and Diagnostics for Statistical Analysis

Model checking will only be performed for the primary analysis for each endpoint. If the model assumptions are met for the primary analysis then we will assume that the model assumptions were also met for any subgroup analyses.

### 11.10.1. Statistical Analysis Assumptions

#### 11.10.1.1. Negative Binomial Regression and Poisson Regression

Endpoint(s)	
 
• Annual rate of on-treatment moderate/severe exacerbations
 
• Annual rate of on-treatment severe exacerbations
 
• Annual rate of all on-treatment exacerbations (mild, moderate, severe)
 
• Annual rate of on-treatment moderate exacerbations
 
• Annual rate of on-treatment exacerbations requiring systemic/oral corticosteroids
 
• Annual rate of on-treatment exacerbations requiring antibiotics
 

Analysis	
 
• Negative binomial regression
 
• Poisson regression (moderate/severe exacerbations)
 

 
• The fit of the regression models will be examined using “Q-Q” plots of the standardized residuals. Interpretation of these plots will be aided by the addition of simulated envelopes as proposed by Atkinson (Atkinson, 1985).
 
	

#### 11.10.1.2. Cox Proportional Hazards

Endpoint(s)	
 
• Time to first on-treatment moderate/severe exacerbation
 
• Time to death from any cause (on-treatment)
 
• Time to first on-treatment severe exacerbation
 
• Time to first on-treatment event in the pneumonia AESI group
 
• Time to first on-treatment event in the pneumonia AESI group resulting in hospitalization, prolonged hospitalization or death
 
• Time to first on-treatment event in the pneumonia AESI group or moderate/severe exacerbation
 
• Time to first on-treatment event in the pneumonia AESI group resulting in hospitalization, prolonged hospitalization or death or severe exacerbation
 
• Time to first on-treatment event in the pneumonia AESI group resulting in hospitalization, prolonged hospitalization or death or severe exacerbation or event in the CV AESI group resulting in hospitalization, prolonged hospitalization or death
 

Analysis	
 
• Cox’s proportional hazard model
 

 
• The proportional hazards assumption will be examined by obtaining the Kaplan-Meier estimates of the survival function <math>S(t)</math> over time separately for each treatment group. In addition, the <math>\ln\{-\ln[S(t)]\}</math> plot will be produced.
 
	

**11.10.1.3. Andersen-Gill**

Endpoints	
 
• Time to onset of each on-treatment moderate/severe exacerbations
 
• Time to onset of each severe exacerbation
 

Analysis	
 
• Andersen-Gill model for recurrent events
 

 
• The proportional hazards assumption will be assessed by plotting the estimated log cumulative hazard function against the log of the time to event by treatment group.
 
	

**11.10.1.4. Mixed Model Repeated Measures**

Endpoint(s)	
 
• Trough FEV1
 
• SGRQ total score
 
• Trough FVC
 
• Post-bronchodilator FEV1
 
• FEV1 reversibility
 
• Post-bronchodilator FVC
 
• TDI focal score
 
• CAT score
 
• Mean number of occasions of rescue use per day
 
• Percentage of rescue-free days
 
• Mean number of nighttime awakenings per night
 
• Percentage of days symptoms stopped usual activities
 
• Pulse rate
 
• Systolic BP
 
• Diastolic BP
 
• QTcF
 

Analysis	
 
• MMRM
 

 
• Distributional assumptions underlying the model used for analysis will be examined by obtaining a normal probability plot of the residuals and a plot of the residuals versus the fitted values (i.e. checking the normality assumption and constant variance assumption of the model respectively) to gain confidence that the model assumptions are reasonable.
 
	

**11.10.1.5. Generalized Linear Model**

Endpoint(s)	
 
• Proportion of responders according to FEV1, SGRQ total score, CAT score, and TDI focal score
 

Analysis	
 
• Generalized linear model
 

 
• Pearson residuals will be plotted by using PLOTS=PEARSONPANEL option for the model statement in SAS.
 
	

**11.10.1.6. Analysis of Covariance**

Endpoint(s)	
 
• QTc(F), Trough FEV1 (Sensitivity), SGRQ Total Score(Sensitivity)
 

Analysis	
 
• ANCOVA
 

 
• Distributional assumptions underlying the model used for analysis will be examined by obtaining a normal probability plot of the residuals and a plot of the residuals versus the fitted values (i.e. checking the normality assumption and constant variance assumption of the model respectively) to gain confidence that the model assumptions are reasonable
 
	

**11.10.1.7. Logistic Regression**

Endpoint(s)	
 
• Subject global rating of change in activity limitation
 
• Subject global rating of change in COPD severity
 

Analysis	
 
• Logistic regression
 

 
• .
 
• The score test will be used to assess the proportional odds assumption.
 
	

## 11.11. Appendix 11: Abbreviations & Trademarks

### 11.11.1. Abbreviations

Abbreviation	Description
ADAE	ADaM Dataset for Adverse Events
ADaM	Analysis Data Model
ADCM	ADaM Dataset for Concomitant Medications
AE	Adverse Event
AESI	Adverse Event of Special Interest
ASE	All Subjects Enrolled
ATC	Anatomical Therapeutic Chemical Classification
BDI	Baseline Dyspnea Index
BMI	Body Mass Index
BP	Blood Pressure
bpm	Beats Per Minute
CAT	COPD Assessment Test
CDISC	Clinical Data Interchange Standards Consortium
CI	Confidence Interval
COPD	Chronic Obstructive Pulmonary Disease
CRT	Case Report Tabulation
CSR	Clinical Study Report
CV	Cardiovascular
DBF	Database Freeze
DM	Data Management
DPI	Dry Powder Inhaler
ECG	Electrocardiogram
eCRF	Electronic Case Report Form
EOS	Eosinophil
EQ-5D-5L	EuroQol Questionnaire (five level)
FEV1	Forced Expiratory Volume in One Second
FF	Fluticasone Furoate
FVC	Forced Vital Capacity
GCSP	Global Clinical Safety and Pharmacovigilance
GLM	General Linear Model
GOLD	Global Initiative for Chronic Obstructive Lung Disease
GSK	GlaxoSmithKline
HRQoL	Health Related Quality of Life
IC	Informed Consent
ICF	Informed Consent Form
ICH	International Conference on Harmonization
ICS	Inhaled Corticosteroid
IDMC	Independent Data and Monitoring Committee
IDSL	Integrated Data Standards Library
ITT	Intent-To-Treat
IVRS	Interactive Voice Recognition System

Abbreviation	Description
kg	Kilogram
KR	Kenward and Roger
L	Liter
LABA	Long-Acting Beta-Agonist
LAMA	Long-Acting Muscarinic Receptor Antagonist
LLN	Lower Limit of Normal
LRTI	Lower Respiratory Tract Infection
LS	Least-square
m	Meter
MACE	Major Adverse Cardiac Event
mcg	Microgram
MedDRA	Medical Dictionary for Regulatory Activities
mL	Milliliter
mmHg	Millimeters of Mercury
MMRM	Mixed Model Repeated Measures
msec	Millisecond
NA	Not Applicable
NQ	Not Quantifiable
PD	Protocol Deviation
PDE4	Phosphodiesterase-4
PDMP	Protocol Deviation Management Plan
PK	Pharmacokinetic
PT	Preferred Term
QC	Quality Control
QTcF	QT interval corrected for heart rate by Fridericia's formula
RAMOS	Randomization & Medication Ordering System
RANDALL-NG	GSK Randomization System – Next Generation
RAP	Reporting and Analysis Plan
RMC	Respiratory Medication Class
RTF	Rich Text Format
SAC	Statistical Analysis Complete
SAE	Serious Adverse Event
SDAC	Statistical Data Analysis Center
SDL	Source Data Lock
SDTM	Study Data Tabulation Model
SE	Standard Error
SGRQ	St. George's Respiratory Questionnaire
SGRQ-C	SGRQ for COPD patients
SI	System Independent
SMQ	Standardized MedDRA Query
SOC	System Organ Class
TDI	Transitional Dyspnea Index
TFL	Tables, Figures & Listings
TSCG	Tibco Spotfire Clinical Graphics software

Abbreviation	Description
TTF	Time to First
ULN	Upper Limit of Normal
UMEC	Umeclidinium
VAS	Visual Analog Scale
VI	Vilanterol Trifenatate

